## 5.0 Study Procedures

### 5.1 Study Design

This is a randomized controlled trial that will enroll participants on a rolling basis. Each participant will be enrolled for approximately 1 year. However, participants may also choose to be consented into the associated repository, "Rewards Project Data Repository (MIRB-00982)." Please refer to the attached study flow chart for a visual depiction of study events and timeframe of participant activities. An overview of what the website (portal) looks like and functionality is in the document titled "website mock up," and portal screen shots.

There are two points of randomization. After patients are enrolled in the study, they will be enrolled in the portal. At portal enrollment, they will be randomized to either receive a wireless (Blipcare) or the wireless Blipcare scale and the Connect device. At enrollment all participants will receive the Blipcare wireless scale. There are two different types of scales: wireless Blipcare scales and a non-wireless digital battery powered Taylor scales. The Blipcare scales are wireless scales that transmit weight data through a cellular hub, "Connect." Regardless of the scale the participant receives, all participants will be encouraged to record their weight manually to better keep track of their weight (Appendix N). All participants in all arms will also record their weight into the study portal as outlined below. The participants that receive a Blipcare scale with the Connect device will have their weight recordings sent automatically to research study staff via the Connect device. At the 16-week study visit, participants may be asked to exchange their scales for a Taylor scale, depending on our Blipcare scale inventory. Due to the mechanism of reusing the Blipcare scales and Connects, some participants may only receive Taylor scales, and some participants may be able to keep their Blipcare scales.

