The participant will be registered in the portal by the coordinator under the administrative login. After the participant's login becomes active it will alert the coordinator and participant which scale the participant receives: either a Blipcare scale or a Blipcare scale and Connect (wifi) device. This is done through a randomization table built into the portal. Each participant will receive either a wireless Blipcare scale or wireless Blipcare scale and wifi Connect device (Carematix). Each participant will be given a scale and an extra set of batteries. Upon plugging the Connect device in to an electronic outlet, it will send all weight readings to the Carematix company which will be accessible by the VA study team. Participants may be asked to return their Blipcare Scales and Connect devices at the 16-week study visit. Participants will receive a phone call and text message/email from the coordinator the day before their visit. If they are being asked to return their Blipcare scales they will be reminded of this. If they received a Connect device, they will be asked to return those. They will also receive a reminder postcard the week before their visit (Appendix L.c, and U). This is further described in section 7. Participants in both groups will be asked to enter their weight into the portal each week.

Participants will be counselled to weigh themselves daily, after urinating and before eating. Participants are given a sheet to document their self-reported weekly weight (Appendix N). Appendix N is solely for the participant to use and for their convenience.

The participant will then select the most convenient day of the week to record their weight. If it is less than 7 days from the baseline visit, it will be the following week. If it is exactly 7 days away, they will be given 14 days to start. Even if the participant chooses the next day, the participant's first actual weigh-in day will be the following week, so no matter what the scenario, the participant will always have at least eight days to start the

study. All participants will record their weekly weights in the participant portal (website). This is to give the participants the maximum amount of time to successfully start the study.

Example:

Sunday	Monday	Tuesday	Wednesday	Thursday	Friday	Saturday
		Baseline study visit				
	Monday is the best day for the participant					

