In order to ameliorate the effects of habituation to the reward as Jeffery (2012) suggests, we will improve the perceived odds of winning to a 1-in-4 chance over weeks 8-16. For each patient, we will use a random number generator to randomly sort numbers from 1 to 8 and pick the top two listed numbers as the two weeks on which the patient will receive \$100 for an on-target weight. Veterans who meet all weekly targets will receive \$100 in guaranteed rewards, and \$300 in random rewards, for a total expected earnings of \$400 (average of \$100/month), used in the JAMA, JGIM, and Annals studies described in Table 1. If a patient misses a monthly weight target, their weekly target weight for the remainder of the reward period will be recalibrated so that the patient can still earn rewards if the patient's weight loss trajectory puts them on track to lose 16 lbs. in 16 weeks, if the weight loss does not exceed 4 lbs. per week.

Once the participant completes his/her weight entry in the portal they will immediately be told if they won their reward or not. If the patient withdraws they will receive what they have earned up to that point in time and we will ask them to participate in an interview to better understand why this study didn't work for them. For participants in the financial reward group, they will receive a check in the mail for their reward. Receipt of the check can take between 3-12 weeks. Depending on enrollment, we will either request the check be issued within one week of when it was earned and the participant is notified or we will submit a request at 16 weeks for the participant to be paid then. To collect the reward, we will ask that the patient come to the clinic for an in-person weigh-in with study staff, but we cannot require it. They will receive the reward regardless of their in-person weight. We do this in part because weight can fluctuate throughout the day and because the true test of whether rewards work will be determined at the 16 and 32 week in-person weigh-ins. Knowing there will be a

weigh-in prior to collecting the reward may also reduce the under-reporting of weight. Participants may login to the portal at any time and see how much they have earned (financial or non-financial).

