The participant information for the portal will be pulled from a crosswalk housed on the secure J:drive folder and within the project access database. The portal will only record the unique study ID. This is not associated with the participant at any point until matched with the study crosswalk on the J:drive by study staff. Information that will be within the portal includes: weekly weights and survey responses. The information housed within the portal will downloaded from the website on to the J:drive. The analyst will then identify the participants and their responses by matching the unique study ID with the participant's name. Due to the current extenuating circumstances we are trying to maintain as much data integrity as we can. When a phone visit is done, the participants verbalized weight will be entered into the database and will also be entered into the excel file included with this modification. We are adding the excel file as another way we will be able to indicate which data points were validated during an in person visit compared to a self-reported weight, verbally provided over the phone. This excel file will be store in the folder J:/rewards, titled PhoneVisits[date].

The Carematix system will work the same way. Each scale will be given a unique code. We will keep the crosswalk with the code to the participant's name on the secure J:drive folder. Carematix will only know the unique code and whatever weight readings are recorded by the scale. Carematix will have no information on any participant in the study. Each week research study staff will login to the Carematix dashboard website and download the Excel document of recorded weights. This excel file will then be saved on the secure J:drive folder and then matched with the participant's name and loaded into the project access database. All matching of study data and participants will only occur within the study team and will not be shared or transmitted with anyone else.

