#### Demographics):

VA MOVE11 partial survey: The survey is the standard enrollment intake survey of the MOVE! program. It covers, height, weight, BMI, ethnicity, race and various health behavior and lifestyle indicators, Regulation of eating behavior survey (REBS): Questions to determine the internal motivation or regulation of a behavior.

Health status from the SF12

Additional sleep and alcohol questions

Financial distress questions from the Prawitz Financial Distress Scale

Three factor eating questionnaire (TFEQ-18): Questions regarding eating patterns and behaviors.

Personal Health Questionnaire Depression Scale (PHQ-8): This is an established diagnostic and severity measure for depressive disorder in large scale clinical trials.

International physical activity questionnaire (IPAQ): Activity level over 7 days, from vigorous, moderate, walking and sitting.

Weight Efficacy Lifestyle Questionnaire Short Form (WEL-SF): Confidence level in controlling certain behaviors

Food insecurity questionnaire (from NHIS): Eating behaviors and food purchasing behaviors based on financial stability and socio-economic status.

NHANES Weight Loss Strategies: Covers a variety of common methods used for weight loss and participants use of them.

Additional Questions: These questions ask a participant why they want to lose weight and how motivated they are to lose weight.

Participants will complete the survey at all four points in the study through the online patient portal (baseline, 16 weeks, 32 weeks, one year). Participants will complete the surveys in the participant portal. The information from the survey will then be downloaded from the secure Austin server and saved directly into the J:drive access database.

**5.5.c. Weight measurements.** Participant weights will be taken at the in-person visits. The participant will be asked to step onto a scale. The weight shown on the scale will be recorded. After the participant, has completed the survey instrument and had their weight taken, they will be randomized to one of three groups, as described in section 5.4. Weight measurements will be taken at all four in-person visits. Participants will also be counseled to weigh themselves daily before eating and after using the bathroom and recording their weight weekly into the portal.

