Hypothesis 1c implies a test of superiority and will be assessed using two-sided tests of  $(\beta_3 = \beta_2)$  in comparisons of weight change from week 16 to week 32 and 12 months, respectively. We will use weight change at week 16 in place of weight at baseline in equation 1, such that differences in weight regain between treatment arms will be adjusted for weight lost over weeks 1-16.

Because all secondary outcomes are continuous variables, a similar equation will be used to assess changes in secondary outcomes. These analyses explore how rewards affect constructs that are believed to mediate the effect of rewards on weight loss.

Missing weight measures will be imputed using data from patients' medical records for routine medical visits and methods developed and tested via simulation by [name] et al. These methods involve estimating longitudinal mixed-effects linear models of weight collected both through the trial and at routine clinic visits as a function of polynomials of time since enrollment, with random components for patient intercept and time, and using the predicted values from this model for any post intervention day as an estimate of what the patient's weight would have been on that day if he/she kept their follow-up appointment.

We assumed a standard deviation of 11.0 lbs. for weight loss based on the results of the JAMA (2008) and JGIM (2011) trials that were conducted in the VA and demonstrated statistically significant differences in

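### The imputation model in 5.6.a has no term for where a weight was measured, so imputed visit weights may carry a modest source offset into the reward-versus-usual-care contrast

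*Combined protocol and SAP*

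**What the plan says.** Section 5.6.a (Data Analysis) states that "Missing weight measures will be imputed using data from patients' medical records for routine medical visits". It then describes fitting mixed-effects "models of weight collected both through the trial and at routine clinic visits as a function of polynomials of time since enrollment". The only random terms it names are a patient intercept and a patient time effect. The model's prediction for the day in question is to represent the weight the patient would have had at a kept follow-up appointment. The method is attributed to a cited paper on imputing trial data from medical charts.

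The weight it replaces is a staff measurement. Section 5.5.c says "Weight measurements will be taken at all four in-person visits".

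The trial also holds weights from other sources:

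- **Portal self-reports.** Section 5.1: "All participants in all arms will also record their weight into the study portal as outlined below". These are home weights under their own instructions (5.1.a): "Participants will be counselled to weigh themselves daily, after urinating and before eating".
- **Phone visits from March 2020.** Section 5.1.b adds a file to show "which data points were validated during an in person visit compared to a self-reported weight, verbally provided over the phone".
- **Routine clinic weights.** Section 9.1.d plans to explore whether these could replace study weights, using a model with time, arm and arm-by-time terms.

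The plan anticipates misreporting. In the financial-reward text of 5.1.a it remarks that a "weigh-in prior to collecting the reward may also reduce the under-reporting of weight", and 9.1.d compares self-reports with wireless-scale readings. Neither check, nor the phone-visit file, is linked to the imputation model.

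**The concern.** The model's named terms are time polynomials and random patient intercept and time. With nothing to mark source, it treats a chart weight and a staff-measured study weight on the same day as two readings of one quantity. If clinic weights run heavier or home weights lighter, the difference passes into the prediction, which is then used as a study-visit weight. Section 9.1.d leaves the interchangeability of chart and study weights open; the imputation assumes it.

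There are two routes by which an offset could reach the comparison with usual care. First, if one arm has more missing visits, even an offset shared by all arms does not cancel. Second, if self-reports enter the model, only the reward arms gain from a low report in weeks 1-16, because the reward follows the portal weight whatever the clinic scale shows. Hypothesis 1a at week 32 and the usual-care condition in hypothesis 1b at week 16 are the tests exposed.

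**Working it through.** **1. Yardstick.** Inputs from 5.6.a: SD 11.0 lb, two-sided alpha 0.025, 80% power, 80 versus 100 patients.

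- SE of the contrast = 11 × √(1/80 + 1/100) = 1.65 lb.
- Detectable difference = (2.241 + 0.842) × 1.65 = 5.09 lb; the plan states 5.1 lb.

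**2. Hand calculation.** Only patients with a missing visit weight are affected. If a share m of an arm is imputed and each imputed value carries an offset d, the arm mean shifts by m × d. The contrast shifts by m(reward) × d(reward) − m(control) × d(control). Offsets are assumptions throughout; 20% is the plan's loss-to-follow-up figure.

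- Same offset, same missingness: 0.
- Chart weights 3 lb heavy, missing 15% reward and 30% control: 0.15 × 3 − 0.30 × 3 = −0.45 lb, favouring rewards.
- Self-reports included, reward arms under-reporting by 1, 2 or 4 lb, 20% missing: 0.2, 0.4 or 0.8 lb, which is 4%, 8% or 16% of 5.1 lb.

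These assume the full offset reaches every imputed value. Staff-measured weights in the model dilute it.

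**3. Simulation with self-reports included.** Setup: 80/100/100 patients, no true effect, 20% missing follow-up visits. Home weights were 2 lb low and chart weights 1 lb high in all arms, with about two chart weights per patient. The model was quadratic in time with random intercept and slope, variances taken as known, 25 runs. Entries are bias in reward minus usual-care weight change (lb); simulation SE 0.03-0.04.

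| Extra reward-arm under-reporting | Week 16 | Week 32 |
|---|---|---|
| None | −0.03 | −0.01 |
| 1 lb, weeks 1-16 | −0.11 | +0.01 |
| 2 lb, weeks 1-16 | −0.20 | +0.02 |
| 4 lb, weeks 1-16 | −0.37 | +0.06 |
| 2 lb, through week 32 | −0.38 | −0.42 |
| 4 lb, through week 32 | −0.73 | −0.83 |

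With home weights left out, bias was 0.05 lb (SE 0.04) at week 16 and 0.12 lb (SE 0.07) at week 32, within simulation error of zero.

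**4. Simulations with 3 lb offsets.**

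- Chart weights 3 lb heavy, no portal data: 0.03 lb with balanced 20% missingness (within simulation error); 0.34-0.37 lb with 30% control and 15% reward missing.
- Reward-arm under-reporting: 0.1-0.3 lb at week 32. With every missing patient a dropout before week 32 (25% missing), it was 0.18 lb at week 32. At week 16, 3 lb of under-reporting gave 0.47 lb, the largest figure at this offset.

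**5. Effect on the test.** A bias of 0.4 lb is 0.4/1.65 = 0.24 SE and moves the two-sided type I error from 0.025 to 0.029. At 0.8 lb it would be 0.043.

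**6. Whether source terms are enough.** With no true effect, a source term removes a simple chart offset. It is not enough otherwise:

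- In the 0.47 lb case, source and source-by-arm terms alone left 0.28 lb.
- With a true 8 lb effect, 25% dropout, portal data and no offsets, week-16 bias toward the null was 0.85 lb under the plan's model and 0.93 lb with source and source-by-arm terms. Adding arm-by-time terms brought it to about 0.02 lb.
- With a true 8 lb effect, 20% missing and visit and chart weights only, the effect was pulled toward zero by 0.55 lb at week 32 when arm terms were absent.
- With source, source-by-reward (allowed to change at week 16) and reward-by-time terms, every scenario in the table gave −0.03 lb at week 16 and 0.00 lb at week 32.

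**The case against.** The best defence is that the plan never says home self-reports enter the model. The sentence introducing the imputation names only medical records as the added data, the cited paper's title concerns charts, and 5.5.c defines study weights by the in-person visits. This stands: a reader might infer that weekly portal entries are pooled with staff weights, but the text permits that without stating it. If they stay out, the under-reporting route closes for portal data.

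A second defence is that 5.6.a summarises a published method, which may handle source. That cannot be settled from these documents; the terms the plan itself lists do not.

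A reader might also infer that offsets do differ by arm, or that the week-32 primary result is materially distorted. Neither is supported. No offset of any size is documented, and all arms receive the same weighing instructions. Nothing suggests that chart weights differ by arm. From week 17 the token rewards do not depend on the weight reported, and under-reporting confined to weeks 1-16 left at most 0.06 lb at week 32 in the table above. Larger week-32 figures need misreporting that outlasts its motive, early dropout, or unequal missingness.

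Finally, equal offsets in the two reward arms cancel in the 1b margin comparison and in the test specified for 1c. That also stands.

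What survives is the route that needs no portal data: chart weights are in the model by name, without a term that puts the prediction on the study-visit scale.

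**Conclusion.** The point holds as a modest, avoidable weakness in a stated model. Imputed visit weights may be biased if sources are offset. The bias reaches the reward-versus-usual-care contrast when missingness differs by arm, or if self-reports enter and reward-arm participants under-report. With assumed offsets of about 3 lb and 15-30% missing, it is about 0.1-0.4 lb, or 0.1/5.1 = 2% to 0.4/5.1 = 8% of the detectable difference; one week-16 early-dropout setting reached 0.47 lb. It is near zero when offsets are common to all arms and missingness is balanced. All sizes rest on assumed offsets, and the unequal-missingness figures on an assumed 30%/15% split.

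The bias is small against a 1.65 lb standard error. The case for acting is that the remedy costs little, and that leaving open which weights enter the model lets the choice be made after the data are seen.

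**What to change.** In 5.6.a:

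- State which weights enter the imputation model.
- Fit it to staff-measured and chart weights, with a fixed effect for chart source plus arm and arm-by-time terms. The chart-weight model in 9.1.d already has the arm terms.
- Predict with source set to study visit.
- If portal or phone self-reports are included, add source and source-by-arm terms for them too. The model that performed well above let the latter change at week 16, when the weight-contingent reward ends.

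The arm-by-time terms belong in the same change, because source terms alone leave bias toward the null when there is a true effect.

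The cost is a few extra parameters and slightly less precise imputations. No new data are needed: phone visits are already flagged, and chart and portal weights come from separate systems. Whether phone-reported weights may serve as observed outcomes is a separate question that this change does not answer.
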